**Aim 2: Pilot CETA delivery at two Zambian HIV clinics (Stage 1B).** Hypothesis 1: *BI+CETA will be clinically ( $d>0.5$ ) and statistically ( $p<.05$ ) more effective in reducing alcohol use and comorbidities than BI alone.* Hypothesis 2: *ART retention and HIV viral load (VL) will improve among recipients of BI+CETA compared to BI alone ( $p<.05$ ).* To test these hypotheses, PLWH who screen positive for hazardous alcohol use will be enrolled. Those with comorbidities and/or who meet criteria for moderate-to-severe alcohol use disorder (AUD) ( $n=160$ ) will be randomized 1:1 to receive BI+CETA or BI alone. Participants who have hazardous alcohol use but do not have a moderate-to-severe AUD and do not have mental health comorbidities will receive a BI and be assessed but not included in the pilot RCT (they will be included in the 'cohort' study). We will measure the difference in change in alcohol use and comorbidities from enrollment to 6-months follow-up and use an Ethyl glucuronide test to confirm self-reported alcohol abstinence. ART retention and VL will also be measured at enrollment and 6 months.

**Aim 3: Investigate feasibility, acceptability, and other implementation factors related to delivery of BI and CETA.** We will describe the care cascade of this approach and identify demographic, clinical, and structural correlates of uptake, engagement, and completion of the BI and CETA. We will investigate implementation factors through mixed methods interviews with study participants and health workers.

**II. Background and Rationale:** Explain why this study is being done. Summarize briefly what is already known about the issue and reference previously published research, if relevant.

- Hazardous alcohol use is common and increasing among persons living with HIV (PLWH) in sub-Saharan Africa (SSA). Alcohol is the most commonly consumed and distributed substance in SSA and prevalence of alcohol consumption is increasing rapidly. PLWH face many adversities, including low social support, trauma exposure, and stigma that increase their risk for hazardous alcohol use and they are between two and four times more likely than the general population to have an alcohol use disorder (AUD).

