Baseline data collection. The baseline assessment will be conducted via ACASI. The participant will first complete the Alcohol Use Disorders Identification Test (AUDIT) to assess eligibility into the study. The ACASI will automatically alert the assessor if the participant is eligible based on the hazardous alcohol use criteria. If eligible, the participant will complete the remaining measures: (1) Center for Epidemiological Studies-Depression Scale (CES-D); (2) Harvard Trauma Questionnaire (HTQ); and (3) the Alcohol, Smoking, and Substance Involvement Screening Test (ASSIST). All of these measures have previously been translated and used by our team in Zambia and the AUDIT, CES-D, and ASSIST measures have been formally validated. A research assistant will be available if there are any challenges with the ACASI. Additionally, we will use HIV clinic files to extract HIV-related data. These data are captured as part of HIV routine care in Zambia and include: (1) ART initiation date, (2) hepatitis B surface antigen, (3) most recent CD4+ count, (4) cumulative and past 6-month ART retention, defined by medication possession ratio (MPR; an objective pharmacy record metric that we have used previously) and (5) plasma HIV viral load (measured at CIDRZ Central laboratory using the Roche COBAS/Ampliprep platform).

Secondary eligibility criteria for the RCT. Following completion of the baseline assessment, ACASI will automatically alert the assessor if the participant is eligible for the pilot RCT via a built-in algorithm. Criteria for the RCT will be (a) AUDIT scores that indicate a moderate-to-severe AUD ( $\geq 12$  for women;  $\geq 16$  among men) and/or (b) meeting validated symptom criteria for depression ( $\geq 16$  on CES-D), trauma/anxiety ( $\geq 2.5$  on HTQ), and/or substance use ( $\geq 27$  for any non-tobacco substance on ASSIST).

Randomization. Participants eligible for the pilot RCT will be randomized 1:1, stratified by sex, to receive the BI alone or BI+CETA. Participants who are NOT eligible for the pilot RCT will be provided with a BI but will not be randomized.

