Follow-up assessments. Alcohol and comorbidities will be assessed in all participants at 6 months (i.e., endline) after baseline. The ACASI questionnaire that was used at baseline will again be administered at this follow-up visit (i.e., the questionnaire at this visit is the same as at baseline). In addition to ACASI assessments, we will confirm self-reports of alcohol abstinence on the AUDIT by conducting a urine-based rapid alcohol biomarker test, ethyl glucuronide (uEtG). Finally, at the 6-month post-assessment, which coincides with a regularly scheduled clinic visit, we will extract relevant information from the client's HIV clinical record (this will be the same information that is collected at baseline), including: , (1) hepatitis B surface antigen, (2) most recent CD4+ count, (4) cumulative and past 6-month ART retention, defined by medication possession ratio (MPR; an objective pharmacy record metric that we have used previously) and (4) plasma HIV viral load (measured at CIDRZ Central laboratory using the Roche COBAS/Ampliprep platform). We will not collect any additional biospecimens for purposes of the study—all HIV-related data will be captured via chart extraction. To supplement retention data captured through MPR measurement, we will also assess visit adherence, the percentage of assigned pharmacy and clinical visits that were made (coming to clinic within 3 days).

Implementation data collection. We will conduct a mixed methods process evaluation with stakeholders involved in the CETA referral and treatment process, including follow-up FGDs and KIIs with participants from Stage 1A and CETA counselors. We will also conduct mixed methods interviews with approximately N=30 PLWH who participated in the Stage 1B pilot RCT. This will include a purposeful sample of PLWH from a range of ages and both sexes who did and did not complete the BI and CETA. Implementation factors to be explored will include: acceptability, appropriateness, reach, cost, feasibility, and sustainability and will explore the attitudes, thoughts, feelings, and barriers and facilitators related to implementation. Interviews will include an in-depth interview component and JHU quantitative implementation measures.

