Study Phase	Activity	Year 1				Year 2				Year 3			
		Q 1	Q 2	Q 3	Q 4	Q 1	Q 2	Q 3	Q 4	Q 1	Q 2	Q 3	Q 4
Planning	Study protocol finalization and ethical approval												
	Staff hiring and site preparation												
	Training of qualitative data staff												
Stage 1A	Focus groups and key informant interviews												
	Adaptation of CETA for PLWH												
	Development of CETA protocol in HIV care based on Stage 1A												
	CETA/mhGAP-IG trainings, assessor trainings, M&E trainings												
Stage 1B	CETA pilot cases												
	Recruitment, consent, screening and baseline assessments (ACASI, HIV)												
	Interventions active												
	Post-treatment assessments (ACASI, UEtG)												
	6-month outcomes assessment (ACASI, UEtG, HIV outcomes via chart review)												
Analysis, dissemination, and next steps	Implementation data collection (PLWH, clinic staff, policy officials)												
	Data analysis												
	Report/manuscript writing and dissemination at conferences												
	Preparation and submission of follow-up R01												

- Provide a brief data analysis plan and a description of variables to be derived.

*Analysis of treatment uptake and completion.* We will estimate a logit model with a binary outcome (1=completer; 0=non-completer) to assess predictors of treatment completion. Predictors will be demographic (e.g., sex, age), clinical (e.g., symptom severity), and structural (e.g., distance from clinic) level factors.

*Analysis of ACASI outcome data.* Analyses will be intent-to-treat. AUDIT score, along with other continuous secondary outcomes (Past 30-Day TLFB [% days drinking and mean drinks per day], CES-D, HTQ, ASSIST scores) will be modelled with linear mixed models. Fixed effects will include treatment arm (0=BI; 1=BI+CETA), time (0=Baseline; 1=6-months post-baseline), and interaction terms between treatment arm

and time. This will allow estimation of the mean difference in change in score between arms and 95% confidence intervals. Cohen's D will be calculated to estimate effect size. Covariates will be included if they differ meaningfully at baseline or predict significant change in the outcome. For dichotomous outcomes or non-normally distributed continuous outcomes, generalized linear mixed effects models will be estimated. Paired t-tests will be used to assess within group change among the non-Pilot RCT hazardous drinkers.

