*Analysis of CETA clinical monitoring data.* We will conduct longitudinal data analysis with CMF and TLFB daily estimates of drinking during CETA. Exploratory analysis will examine trajectories of weekly symptom change based on CMF score and number of drinks per day using spaghetti and scatter plots. We will explore the association between baseline client characteristics on symptom trajectories. We will use survival analysis to calculate the number of sessions required for 25%, 50%, and 75% of clients to achieve one or two standard deviation(s) in symptom improvement from baseline. We will also calculate the percentage of clients that achieve these changes by the end of treatment. Collectively, these analyses will provide insight into *when* symptoms change over the course of treatment, which may be useful in refining CETA in future studies.

*Analysis of HIV outcome data.* In both RCT and non-RCT participants, we will use a linear model to investigate changes to MPR during the period before and after the intervention and a logistic model for changes to the proportion with HIV viral suppression (defined as <1000 copies/ml, the standard in SSA). We will compare visit adherence between those randomized to BI+CETA versus BI alone. Because of the relatively small sample sizes in this pilot study, these data will be primarily descriptive; however, these data will inform a follow-up grant.

*Analysis of uEtG results.* The purpose of uEtG testing is to confirm abstinence and not to validate AUDIT scores >0. Based on Preliminary Studies we expect to identify 'under-reporters,' defined as participants who report abstinence on AUDIT or TLFB and test uEtG-positive. In a secondary analysis, we will exclude under-reporters and re-assess the impact of the intervention on alcohol use and other outcomes.

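### Hypothesis 2 is a between-arm claim on ART retention and viral load at p<.05, but the HIV analysis states no arm comparison for MPR or viral suppression

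*Combined protocol and SAP*

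**What the plan says.** **The hypothesis.** Section I, Aim 2, Hypothesis 2 predicts, at p<.05, that "ART retention and HIV viral load (VL) will improve among recipients of BI+CETA compared to BI alone". The text that follows says participants are enrolled and randomised in order to test Hypotheses 1 and 2.

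**The endpoints.** Section V, Baseline data collection, lists "cumulative and past 6-month ART retention, defined by medication possession ratio", and Follow-up assessments uses the same definition. Viral load comes from the clinic record: "all HIV-related data will be captured via chart extraction". Visit adherence is an addition: "To supplement retention data captured through MPR measurement, we will also assess visit adherence".

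**The analysis.** Under Analysis of HIV outcome data, for RCT and non-RCT participants together, the plan says "we will use a linear model to investigate changes to MPR during the period before and after the intervention", and gives a logistic model for change in the proportion below 1000 copies/ml. It then says "We will compare visit adherence between those randomized to BI+CETA versus BI alone". It closes: "Because of the relatively small sample sizes in this pilot study, these data will be primarily descriptive".

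**The contrast.** Under Analysis of ACASI outcome data the arm structure is explicit: "Fixed effects will include treatment arm (0=BI; 1=BI+CETA), time (0=Baseline; 1=6-months post-baseline", plus their interaction. That paragraph lists AUDIT, TLFB, CES-D, HTQ and ASSIST. Its intent-to-treat statement and its rule for dichotomous outcomes sit under the same heading.

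**The concern.** The hypothesis asks whether adding CETA improves MPR and viral load over BI alone. The stated models ask whether MPR and suppression changed over time. Every RCT participant receives BI and continues routine HIV care, so change over time mixes any CETA effect with both of these and with regression to the mean. Including the non-randomised cohort, which gets no CETA, moves the model further from the randomised question.

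As written, one of the two Aim 2 hypotheses has no pre-specified randomised contrast on its named endpoints. Analysts could choose between a before/after result and a between-arm result after seeing the data. The p<.05 criterion also implies a confirmatory test that the plan's own paragraph disowns and that the sample size was not set to support.

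**Working it through.** **1. Hypothesis against analysis**

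| Outcome | Hypothesis 2 | Stated analysis | Arm term named? |
|---|---|---|---|
| ART retention (MPR) | BI+CETA vs BI, p<.05 | Linear model, before/after | No |
| Viral load | BI+CETA vs BI, p<.05 | Logistic model, change in proportion <1000 copies/ml | No |
| Visit adherence | Not named | Compared by arm, no test given | Yes |

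The ACASI paragraph does not fill the gap. Its heading and outcome list cover questionnaire data, MPR and viral load are chart data, and the HIV paragraph gives them separate models. There is also a smaller mismatch: the hypothesis names viral load, while the analysis uses suppression.

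**2. The plan's own sample size (Section III.B)**

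Inputs: AUDIT effect size d = 0.5, α = 0.05, power 80%, loss 20%. Sidedness is not stated; two-sided reproduces the figure.

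- Normal approximation: n = 2(1.960 + 0.842)²/0.5² = 62.8, so 63 per arm.
- Two-sample t-test: 63.8, so 64 per arm and 128 in total, as stated.
- After loss: 128/(1 − 0.20) = 160, or 80 per arm, as stated.

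Nothing in this calculation refers to MPR or viral load.

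**3. What an arm comparison of suppression could detect**

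The documents give no suppression rate, so BI-arm rates of 60–85% are assumed. By the arcsine method, the detectable shift is h = (1.960 + 0.842)·√(2/n), and the BI+CETA rate is p₂ = sin²(arcsin√p₁ + h/2). At n = 64, h = 0.495. For p₁ = 0.70, 2·arcsin√0.70 = 1.982; adding 0.495 gives 2.478, and sin²(1.239) = 0.894, a difference of 19 points.

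Power for a 10-point gain is Φ(h₁₀·√(n/2) − 1.960), where h₁₀ = 2·arcsin√(p₁ + 0.10) − 2·arcsin√p₁. The 95% CI half-width at equal rates is 1.96·√(2p₁(1 − p₁)/n).

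| Assumed BI-arm rate | Detectable, 64/arm | Detectable, 80/arm | Power for +10 points, 64/arm | CI half-width, 64/arm |
|---|---|---|---|---|
| 60% | 22 points | 20 | 22% | 17.0 points |
| 70% | 19 | 18 | 26% | 15.9 |
| 80% | 15 | 14 | 36% | 13.9 |
| 85% | 13 | 12 | 50% | 12.4 |

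The pooled z-test at 64 per arm gives detectable differences of 22, 20, 16 and 14 points (rounded), and power of 22%, 26%, 35% and 47%. If routine viral loads were available for only 50 per arm (assumed), the arcsine and pooled methods together give about 25, 21–22, 17 and 14–15 points.

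Adjusting for baseline suppression helps modestly. In a simulation with 64 per arm (3000 runs; sex not simulated), power for 70% vs 80% was 26% at a latent pre/post correlation of 0.3 and 33% at 0.7.

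**4. MPR**

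With 64 per arm the t-test detects 0.50 SD at 80% power (0.45 SD with 80 per arm). Baseline adjustment multiplies this by √(1 − r²). From 0.499 SD, r = 0.3, 0.5 and 0.7 (assumed) give 0.48, 0.43 and 0.36 SD.

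**The case against.** The best defence is that the comparison is stated in Aim 2 and only a model term is missing from what the form asks to be a brief analysis plan. The arm term is not excluded, and a reader could assume it was meant. That is fair, and a one-sentence edit would settle it. But the sentence covers the non-randomised cohort as well, and the next one names the arms for visit adherence alone, so the omission reads as more than brevity.

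Second, retention does have one arm comparison, through visit adherence. True, but the plan defines retention by MPR and calls visit adherence a supplement.

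Third, the plan already concedes low power by calling these data descriptive, with AUDIT as the primary endpoint. This stands, and it limits the seriousness. It does not remove the conflict with p<.05, and a descriptive analysis of a randomised pilot can still report the arm difference with its interval.

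Fourth, a CETA effect can be estimated later without new data, since both outcomes are extracted for everyone. Correct: what is lost is pre-specification, not the data.

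Fifth, 64 per arm may be pessimistic, because a missed study visit need not remove chart data. At 80 per arm, power for a 10-point gain is 26%, 31%, 43% and 59% at the four assumed rates. The conclusion is unchanged.

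**Conclusion.** The concern holds and should be fixed. For MPR and viral suppression, the plan specifies no contrast that tests Hypothesis 2, and its descriptive label contradicts the p<.05 criterion. The conclusion rests on the text alone.

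The figures show how little a significance test could add. With 64 evaluable per arm, only differences of about 13–22 points in suppression, or 0.50 SD in unadjusted MPR, are detectable at 80% power. These depend on assumed BI-arm suppression of 60–85%. A non-significant result would say little, so estimates with intervals are the useful output for the planned follow-up grant.

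**What to change.** In RCT participants only, analysed as randomised:

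- **MPR:** linear model for past-6-month MPR at 6 months on arm, baseline MPR and sex. For participants with under 6 months on ART at enrolment, compute baseline MPR over the days available; if there are none, use a missing-baseline indicator.
- **Suppression:** logistic model for <1000 copies/ml at 6 months on arm, baseline suppression and sex, using the post-randomisation viral load closest to 6 months. Report the number missing by arm, with a sensitivity analysis counting missing as not suppressed.
- **Reporting:** arm differences with 95% confidence intervals. Analyse the cohort separately, as descriptive within-person change.
- **Hypothesis 2:** remove p<.05 and label it exploratory, or state the detectable difference beside it. Say that viral load is analysed as suppression.

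Arm and arm-by-time terms, as in the ACASI models, would also close the main gap; the baseline-adjusted form is preferred, and the missing-data details are secondary.

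The cost is edits to the analysis text and to Hypothesis 2, plus recording the viral load sample date. MPR and viral load are already extracted at both times. The downside is that requiring a post-randomisation sample will leave some viral loads missing, because they come only from routine charts.

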## JHSPH IRB Research Plan for New Data Collection

Use this template for new data collection and if you also will analyze secondary data. Answer the questions below and for numbered sections that do not pertain to your study, retain the section numbers and bolded questions, and write "N/A". Please start typing in the gray boxes provided.

**PI Name:** [name] (JHU) & [name] (UAB)

Site PI (CIDRZ): [name]

**Study Title:** Zambia Common Elements Treatment Approach Pilot Study (ZCAP)

**IRB No.:** 8795

**PI Version No. / Date:** Version 1.2, December 5, 2018

- I. **Aims of the Study:** Describe the aims/objectives of the research and/or the project's research questions or hypotheses.

Alcohol misuse is a major unaddressed barrier to ending the HIV/AIDS epidemic. Hazardous drinking increases HIV transmission, delays antiretroviral therapy (ART) uptake, reduces adherence and retention, and increases mortality. Concerningly, alcohol consumption is increasing in sub-Saharan Africa (SSA) where 65% of persons living with HIV (PLWH) reside. In preliminary studies in Zambia, we found that: (1) 47% of male and 16% of female PLWH had hazardous use during their first year on ART, (2) among Zambians who drank hazardously, over 50% had a more severe alcohol use disorder (AUD) and/or mental health problems, and (3) over 30% reported other substance use (most commonly inhalants). Comorbid mental health or substance misuse, similar to alcohol use alone, can also significantly undermine HIV treatment.

Brief alcohol interventions (BIs), the standard of care and typically only alcohol treatment available at most SSA HIV clinics (including Zambia), can be clinically and cost effective for reducing hazardous alcohol use. However, they were not designed to treat more severe AUD or comorbid mental health/substance use problems (hereafter referred to as 'comorbidities'). When BIs are ineffective in these settings, advanced treatments are virtually non-existent. A more comprehensive alcohol treatment approach is therefore needed to reduce the impact of alcohol misuse on the HIV/AIDS response.

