### Stage 1B:

Study participants will be PLWH who are currently receiving care at one of the two study clinics. Participants will be recruited by their regular care providers (i.e., peer educators, counselors, nurses, physicians) and referred to study staff if they are interested. We anticipate enrolling a total of 320 participants, all of whom have hazardous alcohol use. 50% of them will be lower-risk drinkers who do not have moderate-to-severe alcohol use disorders (AUD) or mental health comorbidity. These participants will be part of the 'Cohort Study'. These will not be randomized. The other 50% will be high-risk drinks due to having either moderate-to-severe AUD or mental health comorbidities, or both. This second group will be randomized into the RCT Study. The minimum age of research subjects will be 18. All subjects will be recruited from our two study clinics. Eligibility will be assessed via audio computer assisted self-interviewing (ACASI).

*Initial* inclusion criteria for overall enrollment (into either the Cohort or RCT study) will be:

- HIV positive
- Receiving HIV treatment services at one of the two study clinics
- Current hazardous alcohol use, defined as an AUDIT score of  $\geq 8$  for men and  $\geq 4$  for women
- Provides informed consent

*Secondary* inclusion for enrollment into the RCT will be:

- AUDIT scores that indicate a moderate-to-severe AUD ( $\geq 12$  for women;  $\geq 16$  among men)
- AND/OR: meeting validated symptom criteria for depression ( $\geq 16$  on CES-D), trauma/anxiety ( $\geq 2.5$  on HTQ), and/or substance use ( $\geq 27$  for any non-tobacco/alcohol substance on ASSIST)

Participants who meet initial inclusion criteria AND secondary inclusion criteria will be eligible for the RCT. Participants who meet initial inclusion criteria but NOT secondary inclusion criteria will be eligible for the Cohort study.

- **Exclusion Criteria:**

Stage 1A: No formal exclusion criteria.

Stage 1B: Study exclusion criteria for Stage 1B (applies to the Cohort study and the RCT) will be:

- HIV negative

- Not receiving care at one of the study clinics
- Currently psychotic or on an unstable psychiatric drug regimen
- Actively suicidal: Suicide attempt or suicidal ideation with intent or plan, or self-harm in the past month.
- Unable to provide informed consent

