### A. **Recruitment Process:**

1. Describe how you will identify, approach, and inform potential participants about your study. Include details about who will perform these activities and what their qualifications are.

Before any data collection begins, community meetings will take place at each site in order to explain the procedures of the study, the risk and benefits, the confidentiality of results, and to allow for any questions. Based on our prior experience using this approach in Zambia, which has featured good relationships with the local population, we do not anticipate difficulties in obtaining community approval.

- Stage 1A: CETA Adaptation

PLWH study participants for Stage 1A will be recruited from their regular care providers at the study HIV clinics in Lusaka. Care providers will be asked to inform their adult patients with a history of alcohol use while on ART about the presence of the qualitative study using a recruitment script (included with this IRB application). Interested participants will be referred to our on-site study assessor. The assessor will explain the study in full and obtain informed consent if the participant is interested. The assessor will obtain contact information from the participant to schedule the focus group discussion, which will happen at a later date. This method will ensure that only patients who express interest in the study to their usual care provider will have any contact with research staff.

Health worker and policy level participants will be contacted by a study assessor and informed about the qualitative study. Due to our team’s ongoing collaborative work with the study clinics and the Ministry of Health, we have an existing sampling frame of stakeholders who we will ask to participate in focus group discussions and key informant interviews. Our study team will contact these stakeholders about participation and explain the purpose of the study. If potential participants are interested, the assessor will obtain informed consent and participant contact details to set up the focus group discussion or key informant interview.

- Stage 1B: Pilot RCT of CETA

Study participants for the pilot RCT will be recruited from two HIV clinics in Lusaka. Participants will be recruited from the general HIV+ patient population at these clinics. While receiving regular care at these HIV clinics, clients will be informed of the pilot RCT by a care provider, which may be their physician, nurse, a

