### Stage 1B: Piloting of CETA referral and treatment in HIV clinics.

[figure not shown]
Stage 1B of the study will be a pilot RCT of CETA delivery in HIV clinics. Our hypothesis is that BI+CETA will be more effective than BI alone at treating severe AUD, mental health, and substance use problems. As such, the two populations targeted for this pilot RCT are those that are 'higher risk', namely: (1) PLWH with hazardous drinking and comorbidities; and (2) PLWH with moderate-to-severe AUD (with or without comorbidities). BI alone is currently the standard of care and only alcohol treatment in Zambia HIV clinics and therefore an appropriate comparison to BI+CETA. Participants in these two groups will be randomized 1:1, stratified by sex, to receive BI+CETA or BI alone. Alcohol, substance use, and mental health outcomes will be assessed at baseline and 6-months post-baseline. Retention on ART and HIV viral suppression will also be assessed at baseline and 6-months post-baseline. These HIV outcomes will be assessed as part of usual HIV care. We will also systematically capture data on intervention uptake, attendance, and completion, clinical monitoring, and implementation factors.

Although our focus is on the feasibility of delivering a higher intensity and potentially more effective therapy (i.e., CETA) for individuals at higher risk, we will also provide BI alone for PLWH who report hazardous alcohol use *without* comorbidities and do not meet criteria for a moderate-to-severe AUD (individuals at 'lower risk', referred to as 'cohort' participants in the consent form) and evaluate their outcomes to lay broad foundation for a stepped care intervention in the future. That is, in a real-world program, these are PLWH who would be initially targeted by BI alone. Although enrolling these participants into an RCT is beyond the scope of this study, we will collect pre/post data on the same outcomes as the pilot RCT participants to estimate within group effects of the BI alone for these lower risk drinking problems.

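### Cohort before/after change in HIV outcomes mixes any effect of BI with the expected early response to recently started ART; report it by time on ART and do not credit it to BI

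*Combined protocol and SAP*

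**What the plan says.** On ART, the Stage 1B inclusion list (section IV) asks only for "Receiving HIV treatment services at one of the two study clinics"; no inclusion or exclusion criterion concerns time on treatment. The eligibility steps in the consent section repeat the same list. The recruitment section adds: "Participants will be recruited from the general HIV+ patient population at these clinics".

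At baseline the clinic file supplies the ART initiation date, viral load, and "cumulative and past 6-month ART retention, defined by medication possession ratio". The same chart items, apart from the initiation date, are extracted again at 6 months.

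The paragraph on HIV outcome data covers randomized and non-randomized participants together. On MPR it says "we will use a linear model to investigate changes to MPR during the period before and after the intervention". A logistic model does the same for the proportion below 1000 copies/ml. The only arm comparison that the paragraph names is "We will compare visit adherence between those randomized to BI+CETA versus BI alone". No restriction, stratum or covariate for time on ART appears, and no use of the initiation date is stated.

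The Stage 1B description says that pre/post data on the same outcomes as in the RCT will be collected in the lower-risk cohort "to estimate within group effects of the BI alone for these lower risk drinking problems".

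**The concern.** A before/after change in an uncontrolled group measures everything that happens over the interval. For a patient who started ART shortly before baseline, the dominant event over the next 6 months is ART itself: viral load is expected to go from unsuppressed to suppressed whether or not a brief intervention was given. Such patients are eligible, and they are plausible enrollees. One of the preliminary findings in the Aims is that "47% of male and 16% of female PLWH had hazardous use during their first year on ART".

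The same patients have no complete past-6-month window for MPR at baseline.

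The plan itself reads cohort change as an effect of BI, and says the HIV data will inform a follow-up grant. The next trial could then be planned on a suppression gain that BI did not produce. A within-arm before/after reading in the RCT has the same weakness.

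**Working it through.** **Figures in the plan.** None is given for the HIV outcomes. The RCT calculation is for AUDIT and reproduces: d = 0.5, two-sided 0.05 and 80% power give 63.8, so 64 per arm; 128/(1 - 0.20) = 160. It is not in dispute. The cohort is 160. Applying the RCT's 20% loss to it (an assumption) gives 160 × 0.80 = 128 followed.

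**Assumptions not in the documents.**
- f, the share of recent ART starters: 5%, 10% or 20%.
- g, the net proportion of recent starters who go from unsuppressed to suppressed. A high case is 0.60-0.80. In a lower case half are already suppressed at baseline and 85% at 6 months, so g = 0.85 - 0.50 = 0.35.
- Other participants: 5% change status in each direction, net zero.
- BI has no effect, and every recent starter has a charted baseline viral load.

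**Apparent rise in suppression = f × g.** The chance of p < 0.05 is simulated for n = 128 with an exact McNemar test, which stands in for a logistic model that the plan does not detail.

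| f | g = 0.60-0.80: rise | p < 0.05 | g = 0.35: rise | p < 0.05 |
|---|---|---|---|---|
| 0 | 0 | 2% | 0 | 2% |
| 5% | 3-4 points | 11-17% | 1.8 points | 5% |
| 10% | 6-8 points | 34-52% | 3.5 points | 13-14% |
| 20% | 12-16 points | 85-96% | 7.0 points | 39-46% |

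The ranges in the last column depend on whether some recent starters also lose suppression.

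**If baseline viral loads are missing.** Let c be the share of recent starters with a charted baseline value. The rise among pairs is f × c × g / (1 - f + f × c). At f = 20%:
- c = 0.5: 0.20 × 0.5 × 0.60 / 0.90 = 6.7 points, and with g = 0.80, 8.9 points; p < 0.05 in 36-55%.
- c = 0.25: 3.5-4.7 points; 11-19%.
- c = 0: no rise; 2%.

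**MPR.** Take a patient 30 days on ART, fully supplied, with a later MPR of 0.90 (assumed).
- Fixed 180-day window: baseline 30/180 = 0.17, so the group mean changes by f × (0.90 - 0.17), or +0.07 at f = 10% and +0.15 at f = 20%.
- Counted from ART start: baseline 1.00, so the change is f × (0.90 - 1.00), or -0.01 and -0.02.

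The sign depends on a rule that the plan does not state.

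**RCT.** Both arms carry the same expected drift, f × g, so the expected difference in change is zero. Simulation with 64 per arm and f from 0 to 20% gives a mean difference of about 0 and a type I error close to 5%.

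**The case against.** Several points on the other side stand.

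- *The randomized comparison is sound.* Hypothesis 2 compares BI+CETA with BI alone. A reader might infer that recent starters bias that comparison. They do not: the drift is balanced in expectation, and chance imbalance is ordinary sampling error that the test already allows for.
- *MPR need not rise.* A reader might take the quoted sentence to mean that MPR will seem to improve. Without a stated denominator the documents support only that the baseline window is incomplete.
- *The size is open.* The upper figures need many recent starters, few of them suppressed at baseline, and a viral load on file for each. HIV data come from chart extraction alone, and the documents do not say that a viral load is on file for a patient who has just started ART. First-year patients feature in one preliminary finding, and not all of them are under 6 months on ART. Nothing shows that many will enrol.
- *The outcomes are secondary.* The plan calls these data primarily descriptive and specifies no significance test of cohort HIV change. The eligibility section gives the cohort's purpose as preliminary data on drinking.

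The last point lowers the priority but does not remove the problem. The Stage 1B description extends within-group estimation of BI to the same outcomes as in the RCT, and a descriptive estimate that leans one way can still mislead planning. The provision for covariates that differ at baseline stands under the ACASI analyses, and adjusting for arm imbalance cannot help a group without a comparator.

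**Conclusion.** The concern holds for the cohort's before/after change in viral suppression, and for any within-arm reading of it in the RCT: both lean towards an apparent benefit of BI. For MPR the baseline measure is incomplete in recent starters, and the direction of the artefact is unknown.

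With 5-20% recent starters, all with a baseline viral load, 128 followed and no effect of BI, the apparent rise in suppression is about 2-16 points overall, and about 2-7 if half are already suppressed. Missing baseline values reduce it further. The share of recent starters is not in the documents, so these are illustrations and not forecasts. A reader might infer from the top of the range that a false finding is likely; the documents do not support that. Nor do they support a claim of bias in the comparison between arms.

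This is a cheap improvement of modest priority.

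**What to change.** Change the paragraph on HIV outcome data, using the ART initiation date already extracted at baseline.

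- **Cohort:** base the main before/after estimates of viral suppression and MPR on participants with at least 6 months on ART at baseline. Show recent starters separately and descriptively, with the number who have a baseline viral load. State that cohort change in HIV outcomes will not be attributed to BI; the restriction removes this one source of drift, but the group still has no comparator.
- **RCT:** keep all randomized participants, state the between-arm comparison for MPR and suppression, and include ART duration at baseline (under 6 months versus 6 months or more) as a covariate for precision. Do not restrict the randomized comparison: that would shrink a small sample to remove drift that randomization already balances.
- **MPR:** state the denominator for patients with less than 6 months on ART.

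The cost is analysis-plan wording and a smaller denominator for the cohort HIV estimates. Eligibility and the AUDIT endpoint are unchanged, and no new data are needed.
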